## **2.10 PROHIBITED MEDICATIONS AND PROCEDURES**

Treatment with the following concomitant medications is *prohibited* during the entire duration of the study:

- Topical tacrolimus and pimecrolimus
- Treatment with a live (attenuated) vaccine
- Treatment with other investigational drugs (besides Bermekimab)
- Treatment with topical corticosteroids or topical calcineurin inhibitors; such agents may be administered during the study only if required for atopic dermatitis rescue. If topical corticosteroids and/or topical calcineurin inhibitors are used during the study, study treatment may continue as planned.
- Treatment with systemic corticosteroids or nonsteroidal systemic immunosuppressive drugs (e.g., cyclosporine, methotrexate, mycophenolate-mofetil, azathioprine, etc.), except if required for atopic dermatitis rescue, or if critically medically needed to treat concurrent medical conditions (e.g., asthma).
  - The use of systemic corticosteroids for indications other than AD should be limited to situations for which, in the opinion of the treating physician, there are no adequate alternatives. They should be used on a short-term basis, preferably for  $\leq 2$  weeks. Longer-term use of corticosteroids should be discussed with the medical monitor or designee and may require discontinuation of study drug. Inhaled, otic, ocular, nasal or other routes of mucosal delivery of corticosteroids are allowed throughout the study.
- Leukotriene inhibitors

- Allergen immunotherapy
- Systemic treatment for AD with an immunosuppressive/immunomodulating substance (including, but not limited to, cyclosporine, mycophenolate-mofetil, IFN- $\gamma$ , azathioprine, methotrexate, or biologics)

Study drug will be discontinued if any of the following are used through week 16:

- Treatment with a live (attenuated) vaccine
- Treatment with investigational drugs other than bermekimab.
- Treatment with systemic corticosteroids or nonsteroidal systemic immunosuppressive drugs (e.g., cyclosporine, methotrexate, mycophenolate-mofetil, azathioprine, etc.)

The following concomitant procedures are prohibited during study participation:

- Surgical procedures
- Concomitant ultraviolet (UV) procedures (phototherapy [NBUVB, UVB, UVA1, or PUVA])
- Tanning in a bed/booth
- Patients are not allowed more than 2 bleach baths per week during study participation

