## **2.11 RESCUE TREATMENT**

Rescue treatment for AD may be provided to patients if medically necessary (ie, to control intolerable AD symptoms) at the discretion of the investigator. Topical calcineurin inhibitors may be used for rescue treatment, but should only be used for problem areas (e.g. face, neck, intertriginous and genital areas, etc). If possible, investigators should attempt to limit the first line of rescue treatment to topical medications. However, if the patient does not respond adequately to topical medications after at least 7 days, systemic medications may be used.

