#### **10.5.3.1 Primary Efficacy Analysis**

For the primary efficacy endpoint, the two bermekimab treatment groups will be compared with placebo. To account for these two comparisons, testing will be done in a sequential manner, each at the 0.05 alpha level. The bermekimab weekly injection group (Group 1) will be compared to the placebo group (Group 3) first. If this test is significant at the 0.05 level, then the bermekimab every other week injection group (Group 2) will be compared to the placebo group (Group 3). Otherwise, the P-value for Group 2 vs Group

3 will be considered nominal. This method to control the type-1 error will only be implemented for the primary efficacy analysis variable.

The number and percentage of patients with Eczema Area and Severity Index-75 (EASI-75) ( $\geq 75\%$  improvement from baseline) at week 16 will be presented by treatment group. Patients who terminate from the study early prior to week 16 will count as non-responders (non-achievers) in the primary efficacy analysis (Non-Responder Imputation). If a patient received rescue medication, the patient will be counted as a non-responder from the start of rescue medication. Additional treatment failure rules and sensitivity analyses will be discussed in the statistical analysis plan.

A Cochran-Mantel-Haenszel (CMH) general association test stratified by baseline EASI severity will be used to compare each bermekimab dose separately with placebo. The primary efficacy analysis population will be the mITT population.

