### **5.2.2. Data Handling Rules**

No imputation will be performed for missing baseline values.

For the main analysis of primary endpoint of EASI-75 response at Week 16, a subject who discontinued treatment will be considered as a non-responder from that point onward. The remaining missing data will be imputed as non-responder. Supplementary analyses will be performed and include (1) using observed data regardless of whether the subject discontinued treatment or have missing data, and (2) data after treatment discontinuation will be considered as missing, missing response will be imputed by multiple imputation methods under the assumption of missing at random. Similar data handling rules (i.e., main analysis with non-responder imputation and 2 supplementary analyses) will also be applied for EASI-75 response over time through Week 16. The following data handling rules will be applied for other endpoints:

Binary secondary endpoints:

- Analyses will be similar to the main analysis of the primary endpoint. A subject who discontinued treatment will be considered as a non-responder from that point onward. The remaining missing data will be imputed as non-responder. Supplementary analyses will be performed for selected endpoint (i.e IGA responses) in the same manner as the primary endpoint.

Continuous secondary endpoints:

- If a subject discontinued treatment, zero will be assigned to improvement or percent improvement. Remaining missing data will not be imputed. A MMRM model will adjust for missing post baseline data and all available data from the 3 treatment groups through Week 16 or from Week 16 through Week 36 will be included. Under the assumption of missing at random (MAR), the missing data will be accounted for through correlation of repeated measures in the model. Supplementary analyses will be performed for selected endpoints (i.e. EASI total score, NRS itch score) and include (1) using observed data regardless of whether the subject discontinued treatment or have missing data, and (2) data after treatment discontinuation will be considered as missing, missing data will be addressed by MMRM model.

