### 5.2.3. Treatment Groups

In the efficacy analyses, FAS will be used and the participants will be analyzed according to the randomized treatment groups they were assigned to, regardless of the treatments they actually received. Unless otherwise specified, efficacy analyses during each of study periods below are in general displayed as follows:

- Analysis through Week 16
  - Efficacy analyses for placebo comparison at Week 16 or through Week 16 will be summarized by randomized treatment group:
    - **Placebo:** Participants randomized to placebo group.
    - **Bermekimab 400 mg q2w:** Participants randomized to bermekimab 400 mg every other week injection group.
    - **Bermekimab 400 mg qw:** Participants randomized to bermekimab 400 mg weekly injection group.
    - **Combined Column:** Combined column which combines the data from the randomized and treated participants who are assigned to bermekimab 400 mg q2w or qw treatment groups.
- Analysis from Week 16 through Week 36
  - Efficacy data from Week 16 through Week 36 will be summarized by the following treatment groups:
    - **Placebo → Bermekimab 400 mg qw:** efficacy in participants randomized to placebo group.
      - ◆ Only placebo participants crossover to bermekimab 400 mg qw and received bermekimab at Week 16 will be included in the summary for the visits after Week 16.
    - **Bermekimab 400 mg q2w:** Participants randomized to bermekimab 400 mg every other week injection group.

- **Bermekimab 400 mg qw:** Participants randomized to bermekimab 400 mg weekly injection group.
- **Combined Column:** Combined column which combines the data from the randomized and treated participants who are assigned to bermekimab q2w or qw treatment groups at baseline.

These presentations allow assessment of efficacy over time between treatment groups.

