#### 5.3.2. Estimands

##### Primary Estimand:

The **Composite Estimand** will be targeted for the primary endpoint. The Composite Estimand for the primary endpoint is defined by the following 5 attributes:

- Treatment:
  - Bermekimab 400mg q2w
  - Bermekimab 400mg qw

- Placebo

Note: treatment regimen includes protocol specified rescue therapy as needed.

- Population: Adult participants with chronic moderate to severe atopic dermatitis present for at least 3 years.
- Variable (Endpoint): EASI-75 binary responder variable at Week 16, where a subject who discontinues treatment is considered as non-responder after discontinuation.
- Intercurrent event: The intercurrent event of treatment discontinuation is addressed by the composite strategy, as reflected in the variable definition.
- Population-level summary: Difference in the proportions of subjects achieving EASI-75 response at Week 16 between the bermekimab and placebo treatment groups.

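### Week 32 responder rates can credit bermekimab with a systemic drug started after Week 16, because the mandatory stop ends at Week 16 and the SAP has no rescue rule

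*Protocol*

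**What the plan says.** **Stopping rule.** Protocol 2.10: "Study drug will be discontinued if any of the following are used through week 16". The drugs listed include systemic corticosteroids and nonsteroidal systemic immunosuppressants, with no restriction by indication. No equivalent rule applies after Week 16. Protocol 5.3 then leaves stopping for disease progression to the investigator's judgement.

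**Permission.** Protocol 2.10 prohibits the same two classes throughout the study, "except if required for atopic dermatitis rescue, or if critically medically needed to treat concurrent medical conditions". Protocol 2.11 adds: "However, if the patient does not respond adequately to topical medications after at least 7 days, systemic medications may be used". Neither sets a week limit. A separate item in 2.10 also prohibits "Systemic treatment for AD with an immunosuppressive/immunomodulating substance" for the whole study and gives no rescue exception, which sits badly with the other two texts. Neither version attaches a scoring consequence. Under SAP 4.5, excluded therapy is a protocol deviation.

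**Scoring.** For the primary endpoint, SAP 5.2.2 says that "a subject who discontinued treatment will be considered as a non-responder from that point onward", and remaining missing data become non-response. The paragraph on binary secondary endpoints repeats this and says those analyses resemble the main primary analysis. SAP 5.4 applies it. Rescue is not named.

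**Rescue in the analysis.** Protocol 10.5.3.1, on the primary analysis, says: "If a patient received rescue medication, the patient will be counted as a non-responder from the start of rescue medication". The SAP does not repeat this. Its primary estimand (SAP 5.3.2) says instead: "Note: treatment regimen includes protocol specified rescue therapy as needed".

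**Arm 3 after Week 16.** SAP 5.2.3: "Only placebo participants crossover to bermekimab 400 mg qw and received bermekimab at Week 16 will be included in the summary".

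**The concern.** The protocol (synopsis and section 3) and SAP 1.2 all describe a study of bermekimab monotherapy. A patient whose skin clears on cyclosporine or prednisone at Week 24 while weekly injections continue is not evidence of a bermekimab response, yet the SAP can count that patient as one at Week 32. The same prescription at Week 10 would have forced study drug to stop and so, in Arms 1 and 2, would have made the patient a non-responder from then on.

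After Week 16, the score depends on whether the investigator chooses to stop study drug, not on a rule fixed in advance. SAP 5.2.3 presents the later displays as a way to compare groups over time, so readers will set the Week 32 columns side by side. At stake are named secondary endpoints in small groups, where one or two patients visibly shift a percentage.

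**Working it through.** **1. The plan's own figure.** The plan states no number for rescue. Its group-size figure reproduces. With p1 = 0.60, p2 = 0.20, mean 0.40, two-sided alpha 0.05 and 80% power (Protocol 10.1):

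n = [1.96·√(2·0.40·0.60) + 0.842·√(0.60·0.40 + 0.20·0.80)]² / 0.40² = (1.358 + 0.532)² / 0.16 = 22.3, so 23 per arm. Power at 23 is 81.2%.

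The 23 is a power requirement, not a count of evaluable patients. About 90 patients are to be randomised 1:1:1, so 90/3 = 30 per arm.

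**2. Tracing one drug through the rules.** Take a systemic immunosuppressant given for AD.

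| | Arms 1 and 2 | Arm 3 |
|---|---|---|
| Use through Week 16 | Study drug must stop (2.10); non-responder from then on, including Week 32 (SAP 5.2.2) | If stopped before crossing over, left out of summaries after Week 16 (SAP 5.2.3, 5.4) |
| Use after Week 16, study drug continued | No mandatory stop; observed value at Week 32 | No mandatory stop; observed value at Week 32 |

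The top row assumes that sites enforce the stop.

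**3. Endpoints reached.** Protocol 3.1 lists 13 secondary families.
- Six are responder endpoints with a Week 32 time point: peak itch, overall itch, peak pain and overall pain NRS, EASI-75 and EASI-90.
- Six are continuous with a Week 32 time point: DLQI, HADS anxiety, HADS depression, POEM, SCORAD and GISS.
- IGA response is at Week 16 only.

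6 + 6 + 1 = 13.

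**4. Denominators.** For EASI-75 and EASI-90 in Arms 1 and 2, the full analysis set with non-responder imputation keeps n near 30 whatever the dropout. Smaller denominators arise in two places:
- The NRS families count only patients with a baseline score of at least 4. Entry (Protocol 4.1) requires only peak itch of at least 3 and sets no minimum for overall itch or pain.
- The Arm 3 column counts only patients who crossed over.

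**5. Size.** If k users stay on study drug and a fraction r of them respond at Week 32, observed scoring exceeds non-responder scoring by 100·k·r/n points.
- One responder, n = 30: 100/30 = 3.3 points (for example 18/30 = 60.0% against 17/30 = 56.7%).
- Three responders, n = 30: 18/30 = 60.0% against 15/30 = 50.0%.
- Assumed range, k = 1 to 5 and r = 25% to 100%, n = 30: 0.25/30 = 0.8 points to 5/30 = 16.7 points.
- One responder in an NRS family or the Arm 3 column: 100/23 = 4.3 points or 100/15 = 6.7 points, with 23 and 15 as assumed denominators.

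These are upper bounds on what the other drug contributed, because a user might have responded anyway.

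**The case against.** **Observed scoring is a choice, not an oversight.** SAP 5.2.2 ties binary secondary endpoints to the primary approach, in which rescue is part of the regimen and discontinuation is the only intercurrent event. This largely stands: observed scoring follows from the SAP's logic. But through Week 16 that logic works alongside a stop rule that turns use of these two classes into non-response. After Week 16 the stop rule is gone, and no estimand is written for Week 32.

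**A reader might infer that the plan scores the same drug by two opposite rules.** It does not. One discontinuation rule applies throughout. A patient taken off bermekimab differs from one still dosed, and the Arm 3 omission is the general crossover rule. The difference comes from where the mandatory stop ends.

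**A reader might infer that the primary result is affected, or that the same before/after split applies to biologics, other immunomodulators and phototherapy.** The documents support neither. The comparisons specified in SAP 5.4 are at Week 16, with later visits summarised. Those other therapies are not clearly on the stop list.

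**Protocol 10.5.3.1 already counts rescued patients as failures.** That sentence sits under the primary analysis. Protocol 10.5.3.2 carries over only the CMH test, and the SAP drops the rule. Read broadly, it would put protocol and SAP in conflict at Week 32 as well.

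**Listings suffice.** SAP 4.6 lists patients who received treatment that could improve AD, and SAP 4.5 summarises deviations. Both help a reader find affected patients, but neither changes a reported rate. Discretionary stopping under Protocol 5.3 may reduce the number affected.

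**Conclusion.** The point holds and is minor. A patient who starts a systemic corticosteroid or nonsteroidal systemic immunosuppressant after Week 16 and remains on bermekimab is scored as observed, and may count as a bermekimab responder, in the six Week 32 responder families.

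The effect is confined to descriptive rates without concurrent placebo. It is 3.3 points per affected responder for EASI-75 and EASI-90 in Arms 1 and 2, assuming 30 per arm. It is larger only in the NRS families and the Arm 3 column, by an amount that depends on unknown denominators. The total is unknown because the documents give no rate of use.

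**What to change.** In SAP 5.2.2 and 5.4, for binary secondary endpoints at visits after Week 16 through Week 32 only, count a patient as a non-responder from first use of either of the following, whether or not study drug was stopped:
- a systemic corticosteroid or nonsteroidal systemic immunosuppressant for any indication, to match the stop list in Protocol 2.10;
- any other systemic AD therapy, or phototherapy.

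Keep observed-value scoring as a supplementary display. State three limits in the text:
- The Week 16 primary estimand is not changed by this rule.
- Topical rescue stays part of the regimen.
- The separate conflict between Protocol 10.5.3.1 and SAP 5.3.2 on rescue for the primary endpoint must be settled on its own.

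**Cost.** One or two SAP sentences and one display. No new data are needed: the protocol synopsis has concomitant medications and procedures collected to the end of study. Even the narrower calendar footnote (7 days after the last dose) reaches Week 32 for a patient dosed at Week 31 (Day 217 + 7 = Day 224).

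**Downsides.** Week 32 rates will be slightly lower, and with topical rescue still allowed they will not be pure monotherapy rates. The rescue rule after Week 16 will differ from the Week 16 primary estimand and from the continuous endpoints, which are left as planned.

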## **2.11 RESCUE TREATMENT**

Rescue treatment for AD may be provided to patients if medically necessary (ie, to control intolerable AD symptoms) at the discretion of the investigator. Topical calcineurin inhibitors may be used for rescue treatment, but should only be used for problem areas (e.g. face, neck, intertriginous and genital areas, etc). If possible, investigators should attempt to limit the first line of rescue treatment to topical medications. However, if the patient does not respond adequately to topical medications after at least 7 days, systemic medications may be used.

## **3. STUDY DESIGN AND OBJECTIVES**

This is a phase II, randomized, double-blind, placebo-controlled study to further establish the efficacy and safety and explore dose effects for bermekimab monotherapy in adults with moderate to severe Atopic Dermatitis (AD). Patients will be assessed for study eligibility at the initial screening visit after providing informed consent. Thirty days are allowed in the screening window to complete all screening procedures and randomize the subject. During the screening period, certain treatments will be washed out, as

applicable, according to eligibility requirements. Patients who fail initially may be re-screened once based on the investigator discretion but only if inclusion criteria are met at time of re-screening.

The study is approximately 40 weeks (30 day screening period, 32-week treatment period and a 4-week follow-up period) for all subjects.

Patients who meet the eligibility criteria at screening will be randomized in a 1:1:1 ratio to one of two treatment arms or placebo:

- Arm 1: 800 mg of bermekimab + placebo loading dose (2mL SC injection containing 400 mg of bermekimab and one 2mL SC injection of placebo) at week 0 followed by weekly (qw) subcutaneous (SC) injections of 400 mg bermekimab through week 31
- Arm 2: 800 mg loading dose of bermekimab (2 x 400 mg SC injections) at week 0 followed by subcutaneous (SC) injections of 400 mg bermekimab every other week (q2w) alternating with matching placebo q2w through week 31
- Arm 3: 4mL loading dose of placebo (2 x 2mL SC injections) at week 0 followed by weekly placebo injections from weeks 2 through week 15. Patients in Arm 3 will begin to receive weekly (qw) blinded subcutaneous (SC) injections of 400 mg bermekimab beginning at week 16 through week 31.

In order to maintain blinding, all patients will receive two injections at week 0 and 16, followed by weekly injections from week 1 to 31. Additionally, at least one qualified individual will be designated at each study site to perform all preparation and injection of the investigational product. The designated injector(s) should have no other contact with the participant during the study, should not discuss the participant's treatment with the participant, participant's caregiver, or other site personnel at any time, and will not be permitted to review the participant's medical records, questionnaires, or the electronic CRF prior to each injection. The designated injector(s) should be documented in the source documents at each visit.

During the 32-week treatment period, patients will attend weekly clinical study visits. Clinical assessments, collection of samples for bermekimab concentrations, and safety testing will be performed at specified clinic visits. After completion of the 36-week study period, data will be locked and analyzed for safety and efficacy endpoints for all arms. In addition to the analyses that will be performed following the formal database lock at the end of the study at Week 36, an additional database lock may be performed

at Week 16, and interim analyses utilizing unblinded efficacy data available as the study progresses, may also be conducted to help plan potential future development activities. An internal interim analysis committee (IAC) will be established to review the interim data and formulate recommended decisions/actions. The IAC will consist of at least a clinician and a statistician (neither of whom are involved in study conduct or compound development), one of whom will chair the committee, and may also include other members as required by the nature of the IAs. Details will be provided in a separate IAC charter, which will define the organization and roles and responsibilities of the committee, possible recommendations or requests, and the communication process following IA reviews. Results from the Week 16 database lock and/or interim analyses will not be disseminated to investigators or subjects participating in the study. In addition, results of the interim analyses will not be disseminated to individuals associated with the conduct of the study.

Patients will be monitored at a follow up visit (visit 34/week 36) for safety and clinical assessments after completing the 32 week treatment period..

The protocol of the study will be approved by the Institutional Review Board (IRB) or the Ethics Committee (EC) of the participating study sites. Depending on the participating countries both local and central IRB/EC approvals will be granted. The study will be registered at [www.clinicaltrials.gov](http://www.clinicaltrials.gov) before the enrollment of the first patient into the study. The trial will be conducted in compliance with the protocol, GCP, and all applicable regulatory requirements.

